**Table 1: Study scheme**

		Observational period	
		Standard observational period for all observed patients	Prolonged observational period if patients start newly approved drugs between Month 6 and Month 12
Baseline	Month 0 to Month 12	6 months after the start of new therapy (e.g., max observation period of 18 months if patients start the newly approved drugs during the last month of standard observational period).	

The entire observational period will last 12 months. Patients that will start treatment with any newly approved drugs between Month 6 and Month 12 will complete a 6-month observational period after the switch, and therefore the entire observational period in these patients may be prolonged up to a maximum of 18 months. In the context of this study, newly approved drugs are considered all those newly approved

during the study and commercially available for prophylaxis treatment in patients with Haemophilia A without inhibitors.

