- Body Mass Index (BMI) evaluated at baseline and every three months.
- Number of days away from school (patient) and/or work (patient and caregiver), and age of possible early retirement (caregiver) during the observation period, evaluated through administration of questions (evaluated at baseline, every month, and at the end of the study).
- Number of hospitalization days (patient) during the observation period evaluated through administration of questions (evaluated at baseline, every month, at the end of the study).
- Pain intensity measured using a Visual Analogue Scale (VAS) (evaluated at baseline, every month and at the end of the study).

The intensity of pain will be evaluated at baseline, every month and at the end of the study, as well as at each bleeding episode, by means of a 100 mm VAS and will be recorded through ePRO application. The left extreme of the horizontal line means “No pain = 0” while the right extreme means “Worst Pain Imaginable = 100”.

- To evaluate adherence to the treatment regimen: documented during planned visits according to source data (ePRO data) in electronic Case Report Forms (eCRF) by the investigator.

The adherence to the treatment regimen will be analyzed as proportion of “Yes” and “My therapeutic plan does not include any treatment in the last week” on the total of week reported via the ePRO. Missing data for some weeks will be treated as “No”. The total number of weeks will be derived as:

$$(End\ of\ study\ date - Baseline\ date + 1) / 7$$

- To describe the active vs. sedentary haemophiliac patients in terms of:
  - Severity of disease
  - Annualized bleeding rate (ABR)

The annualized bleeding rate will be derived as follows:

$$\frac{\text{total number of bleeds}}{\text{sum of the individual study's durations}}$$

where the individual study's duration will be given by

$$\text{end of study date} - \text{baseline date} + 1$$

- Pain and use of painkillers (as described above).
- Drug regimen adopted (as described above).
- HRQoL (as described above).
- Hospitalization/missed days at school (as described above).
- Joint Health Status (as described above).
- To describe severe vs moderate haemophiliac patients for the above mentioned items.

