The adherence will be summarized as a continuous variable as described in the introduction of Section 4. Moreover, the number and proportion of subjects who have a compliance of at least 80% will be shown.

The adherence to the treatment regimen will be analyzed as proportion of “Yes” and “My therapeutic plan does not include any treatment in the last week” on the total of week reported via the ePRO. Missing data for some weeks will be treated as “No”. The total number of weeks will be derived as the ceil of (End of study date – Baseline date + 1) / 7.

The main reasons for no assumption, change of the dose or frequency will be listed.

Adherence to treatment regimen will also be summarized:

- by start of any newly approved drug for haemophilia (see Section 4.4.4 for subgroup definition).
- by COVID-19 period (see Section 4.4.4 for subgroup definition).
- by month through the entire observational period to observe the impact of COVID-19.

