#### **4.7 MISSING DATA**

The number of patients with missing data will be presented under the “Missing” category, if present. Missing values will not be included in the denominator count when computing percentages. Similarly, only the non-missing values will be evaluated for computing summary statistics for continuous endpoint, without any imputation for missing data. Any exception will be clarified as a note in the related tables.

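### Weeks without an ePRO answer count as non-adherent, so the adherence percentage and its 80% cut mix treatment adherence with app completion, and the SAP's week count is not consistent

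*SAP*

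**What the plan says.** The adherence paragraph of SAP 4.4.2 counts two weekly ePRO answers as adherent: 'Yes', and the answer that no treatment was planned in the past week. It expresses them as a proportion "on the total of week reported via the ePRO". It then adds that "Missing data for some weeks will be treated as" a 'No', and that "The total number of weeks will be derived as the ceil of" the days from baseline to end of study, inclusive, divided by 7.

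SAP 2.2.1 gives the same definition and the same rule for missing weeks. There, "The total number of weeks will be derived as" the same quotient with no rounding.

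Adherence is summarised as a continuous variable, and "the number and proportion of subjects who have a compliance of at least 80% will be shown". It is also shown by start of a newly approved drug, by COVID-19 period and by month. SAP 4.4.3 plans no sensitivity analysis. SAP 4.3.2 summarises compliance with the fitness tracker, but the SAP text plans no such summary for the ePRO.

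**The concern.** Under this rule a patient who takes every planned treatment but skips app entries gets the same score as a patient who answers every week and misses treatments. The output cannot separate the two.

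Incomplete answering is foreseeable. Protocol 6.1.1 describes a monthly reminder about bleeds and their treatment, and no weekly adherence prompt is described. The ITT population in SAP 4.1.3 requires only that the patient received the app and the tracker.

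The period comparisons are the most exposed. If app use falls over follow-up, or differs before and after a switch or during a lockdown, that change would be read as a change in treatment adherence. Separately, two programmers following sections 2.2.1 and 4.4.2 can compute different percentages and place the same patient on different sides of 80%.

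**Working it through.** The documents give no expected adherence or sample size for this endpoint, so there is no stated figure to reproduce. The SAP's own formulas were applied.

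**Inputs.** Threshold 80% (SAP 4.4.2). Missing weeks scored 'No' (SAP 2.2.1 and 4.4.2). Follow-up from SAP section 2: "The entire observational period will last 12 months", taken as 365 days; it "may be prolonged up to a maximum of 18 months" for patients who switch late, taken as 548 days. Weekly completion is not given, so a range of 70% to 100% is assumed.

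**Qualifying weeks needed.**
- 365 days: 365/7 = 52.14, rounded up to 53. 0.80 × 53 = 42.4, so 43 weeks are needed. A fully adherent patient who misses 11 answers scores 42/53 = 79.2%.
- 548 days: 548/7 = 78.29, rounded up to 79. 0.80 × 79 = 63.2, so 64 are needed, and 16 missed answers put a fully adherent patient below 80%.
- The count depends on exact follow-up. At 358 to 364 days there are 52 weeks and 42 are needed (0.80 × 52 = 41.6).

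**Expected score.** If missing answers are unrelated to adherence, the expected score is completion × true adherence, so the two factors enter symmetrically. For example, 0.90 × 0.90 = 0.81.

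**Chance of reaching 80% over 53 weeks.** Weeks are assumed independent. The second column is the exact binomial probability of at least 43 of 53. The last two columns come from simulation (200,000 patients per scenario).

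| Completion | True adherence 100%, missing = 'No' | True adherence 90%, missing = 'No' | True adherence 90%, answered weeks only |
|---|---|---|---|
| 100% | 1.00 | 0.99 | 0.99 |
| 95% | 1.00 | 0.86 | 0.99 |
| 90% | 0.99 | 0.58 | 0.98 |
| 80% | 0.50 | 0.09 | 0.98 |
| 70% | 0.05 | 0.003 | 0.97 |

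On answered weeks, a fully adherent patient with at least one answer always scores 100%.

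**Denominators compared, 365 days.**
- 40 answered weeks, 38 qualifying: 38/40 = 95.0% on reported weeks, 38/53 = 71.7% rounded up, 38/52.14 = 72.9% unrounded.
- 42 qualifying weeks: 42/53 = 79.2% (below the cut) or 42/52.14 = 80.5% (above it).
- If only 52 weekly questions fall in the period, rounding up caps the score at 52/53 = 98.1%. If 53 answers fall in it, the unrounded form gives 53/52.14 = 101.6%.

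**Sub-periods.** The SAP gives only the whole-study formula. If the same rule were applied to the first lockdown period in SAP 4.4.4 (1 March to 4 May 2020, 65 days), 65/7 = 9.29 rounds up to 10 weeks, and three missed answers give 7/10 = 70%. This application is an inference, because the SAP does not state the denominator for these periods.

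**The case against.** Counting missing weeks as 'No' is openly pre-specified and conservative, and SAP 2.2.1 and 4.4.2 agree on it. The endpoint is descriptive, with no test or decision attached, and the continuous summary means the 80% cut is not the only output. Weeks after a patient's end of study are not counted. Investigators review ePRO entries and can follow up with patients (protocol 6.4.1), and all data are listed, so completion could be recovered by hand. An answered-weeks figure has its own bias. All of this stands, and it limits the weight of the point. But a conservative level does not protect a comparison between periods when completion differs between them.

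Three stronger readings are tempting, and the documents do not support them:
- **A contradiction with SAP 4.7.** That section summarises data "without any imputation for missing data", but it also allows exceptions noted in the tables. The rule here is a specific exception to a general default.
- **Reported weeks as a fully live second definition.** The two sentences that follow would have no function if only answered weeks counted, so calendar weeks are the natural reading. The phrase needs correcting, but the firmer conflict is rounding in 4.4.2 against no rounding in 2.2.1.
- **Missing as 'No' is the wrong headline.** The documents give no evidence for choosing between the two figures. That choice is a trade-off.

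**Conclusion.** The point holds. As defined, the adherence percentage and the 80% classification combine treatment adherence with app completion, and nothing planned in the SAP text separates them. Over 365 days with rounding up, 42 or fewer answered weeks make 80% unreachable. The probabilities in the table rest on independent weeks, missingness unrelated to adherence, and an assumed completion range.

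A reader might infer that adherence in this study will be substantially understated, or that completion did change between periods. The documents do not show either, because they give no completion rate; the number of patients affected is unknown. What is established is that a change in completion alone would move the reported figure. The denominator also needs correcting, since rounding alone can reclassify a patient with 42 qualifying weeks.

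**What to change.** 1. State one denominator in SAP 2.2.1 and 4.4.2, remove the reference to reported weeks if calendar weeks are meant, and settle the rounding. Counting the weekly questions due in the period would avoid both the 98.1% cap and values above 100%.
2. Define the denominator for the before/after-switch, COVID-19 and monthly periods.
3. Report weekly ePRO completion overall and for each of those periods.
4. Show adherence over answered weeks side by side with the missing-as-'No' figure, with the latter labelled as a lower bound, overall and in each period comparison.

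The cost is some extra tables from data already collected. The answered-weeks figure assumes unanswered weeks resemble answered ones and may be too high if patients who skip doses also skip entries. For that reason both figures should appear together, and the pre-specified one need not be replaced.

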**To describe the active vs sedentary haemophiliac patients in terms of:**

**Severity of disease**

The severity of disease will be analyzed as described in Section 4.2.7.

**Annualized Bleeding Rate (ABR)**

The total number of bleeds (overall, by site and by type) and the total follow-up (person-years) will be displayed. The rate will be derived as ratio between the number of bleeds and total follow-up.

Number and proportion of subjects with at least one bleeding will be also shown.

The exact Poisson 95%CI for the rate will be calculated overall, by site and type.

Other subgroup analyzes: frequency of physical activity, severity of the disease (see Section 4.4.4 for subgroup definition).

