- Bleeds starting from the first sign of bleed and ending 72 hours after the last treatment for the bleed, within which any symptoms of bleeding at the same location or injections are ≤ 72 hours apart, are considered the same bleed.
- Any injection to treat the bleed, taken > 72 hours after the preceding injection, is considered the first injection to treat a new bleed at the same location.
- Any bleed at a different location is considered a separate bleed regardless of time from last injection.

Definition of bleed sites:

Sites of bleed will be defined as follows:

Target joints: defined as major joints (e.g., hip, elbow, wrist, shoulder, knee, and ankle) into which repeated bleeds occur (frequency of ≥ 3 bleeds into the same joint over the last 24 weeks prior to study entry), - Muscle bleeds, - Other bleeds.

Definition of bleed types:

The assessment of a bleed will be separated into spontaneous bleeds, traumatic bleeds, and bleeds related to procedure/surgery. Both spontaneous bleeds (i.e., the occurrence of haemorrhage where neither the patient nor a caregiver can identify a reason) and traumatic bleeds (i.e., haemorrhage occurring secondary to an event such as trauma, "strenuous" activity, or "overuse") will be collected.

Types of bleed will be defined as follows:

- Spontaneous bleeds: bleeds should be classified as spontaneous if a patient records a bleed when there is no known contributing factor such as definite trauma, antecedent "strenuous" activity or "overuse" or "procedure/surgery." The determination of what constitutes "strenuous" or "overuse" will be at the discretion of the patient. For example, light jogging may be considered "non-strenuous" while sprinting may be considered "strenuous," lifting of weights for a short period of time may be considered "moderate use" while repetitive weightlifting may be considered "overuse."
- Traumatic bleeds: bleeds should be classified as traumatic if a patient records a bleed when there is a known or believed reason for the bleed. For example, if a patient is to exercise "strenuously" and then has a bleed in the absence of any obvious injury, the bleed would be recorded as a traumatic bleed because, although no injury occurred, there was antecedent "strenuous" activity. Bleeds subsequent to injuries would certainly be classified as traumatic.

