## **4. STATISTICAL METHODS**

Appropriate descriptive statistics will be produced, according to the variable. For continuous data n, mean, standard deviation (SD), median, I and III quartile, and range (minimum and maximum) will be presented. For categorical data, frequency distributions and percentages will be presented.

Unless otherwise specified, hypothesis testing (exploratory in nature) will be carried out at the alpha = 0.050 level (two-sided). For all inferential analyses, the p-values will be rounded to three decimal places. Due to the exploratory nature of this study, no adjustment for multiplicity will be made.

Any unplanned analyses as well as deviations from the original SAP will be clearly documented in the Clinical Study Report.

All the data collected and derived in the study will be presented in subject data listings.

With reference to the ePROs and physical activity data (i.e. all data derived from ePRO app and the fitness tracker), only data collected between the informed consent date and Date of patient completion or withdrawal (extremes included) will be analyzed. For the interim analysis, the minimum between Date of patient completion or withdrawal and the cut-off date will be considered as upper bound.

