### **Number, sites and types of bleeds occurring during routine clinical practice and reported at any occurrence via the electronic Patient-Reported Outcome (ePRO) application**

The overall number of bleeds per patients will be analyzed by means of descriptive statistics as described in Section 4. Data will be shown overall and by age group.

Bleeds that occur the same day but in different body site will be counted separately. Number and proportion of patients with no bleeds and 1 or more bleeds will also be shown.

The bleeds will be analyzed overall, by body site (Joint bleeds, Muscle bleeds, Other bleeds) and type (Spontaneous bleeds, Traumatic bleeds, Bleeds related to procedure/surgery).

The 95%CI for the mean number of bleeds will also be shown.

Number, sites and types of bleeds will also be summarized:

- by start of any newly approved drug for haemophilia (see Section 4.4.4 for subgroup definition).
- by COVID-19 period (see Section 4.4.4 for subgroup definition).
- by month through the entire observational period to observe the impact of COVID-19.

Other subgroup analyzes: frequency of physical activity, severity of the disease.

**Treatment regimen for haemophilia A (prophylaxis, preventive treatment before physical activity, treatment for any episode of bleeds), in terms of type of regimen (demand vs. prophylaxis), product used and dose.**

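### The exact Poisson interval on the pooled annualised bleeding rate leaves out between-patient variation, so it is too narrow when the rate is read beyond these patients or used to contrast groups

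*SAP*

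**What the plan says.** SAP 2.2.1 and the ABR part of SAP 4.4.2 define one pooled rate. In 4.4.2: "The rate will be derived as ratio between the number of bleeds and total follow-up". For uncertainty: "The exact Poisson 95%CI for the rate will be calculated overall, by site and type". Activity (active or sedentary) and disease severity follow as subgroup analyses, in a separate sentence that does not mention an interval.

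The part of SAP 4.4.2 on number, sites and types of bleeds summarises bleeds per patient and adds: "The 95%CI for the mean number of bleeds will also be shown". It has the same two subgroupings: "Other subgroup analyzes: frequency of physical activity, severity of the disease". SAP section 4 supplies the descriptive statistics: "For continuous data n, mean, standard deviation (SD), median, I and III quartile, and range (minimum and maximum) will be presented".

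On counting, Protocol 6.4.1 merges repeat symptoms or injections at one location: "Bleeds starting from the first sign of bleed and ending 72 hours after the last treatment for the bleed", with events no more than 72 hours apart treated as the same bleed. Other locations are not merged: "Any bleed at a different location is considered a separate bleed regardless of time from last injection". The SAP agrees: "Bleeds that occur the same day but in different body site will be counted separately".

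**The concern.** An exact Poisson interval uses two numbers only, the total count and the total person-time. It cannot tell 107 patients with two bleeds each from a cohort in which a few patients have most of the bleeds.

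The documents give reason to expect uneven bleeding. The cohort mixes severe and moderate disease, and prophylaxis with on-demand treatment. Some patients will have target joints, which are defined by repeated bleeds. The baseline form (SAP 4.2.7) runs from 0 to more than 6 bleeds in 24 weeks. The 72-hour rule removes part of the clustering within patients, but bleeds at several sites on one day still count separately.

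What is at stake is how the interval is read. The objectives use the ABR to describe active against sedentary and severe against moderate patients, and Protocol 4.1 foresees comparison with other studies. In both uses, variation between patients is part of the uncertainty. Leaving it out overstates precision and can make a chance difference between groups look real.

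**Working it through.** **Inputs from the documents.** 107 patients included (SAP 2.3.1). Follow-up is 12 months, up to 18 after a late switch to a new drug, and shorter after withdrawal (SAP 2, Table 1; Protocol 6.5.1). No ABR, bleed count or variance is stated, so there is no planned figure to reproduce.

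**Assumptions.** Each patient's rate follows a gamma distribution with mean r per year and variance a × r² (a is the dispersion). Counts are Poisson given that rate.

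**Step 1: how much too narrow.** With one year per patient, the variance of a patient's count is r + a r², where the Poisson interval assumes r. The standard error is therefore too small by a factor √(1 + a r), and coverage is approximately 2Φ(1.96/√(1 + a r)) − 1.

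| r per year | a | √(1 + a r) | Approximate coverage |
|---|---|---|---|
| 1 | 0.1 | 1.05 | 94% |
| 5 | 0.1 | 1.22 | 89% |
| 1 | 0.5 | 1.22 | 89% |
| 2 | 1 | 1.73 | 74% |
| 1 | 2 | 1.73 | 74% |
| 5 | 0.5 | 1.87 | 70% |
| 5 | 2 | 3.32 | 45% |

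Simulation with n = 107 and unequal follow-up agrees: about 94%, 90%, 88-90%, 75%, 75%, 70% and 44% in the same order. A patient-level interval covers about 94-95%. For rare site or type rates (0.2 to 0.5 per year, a = 0.5) the exact interval still covers 95% to 93%.

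**Step 2: one worked interval.** Take 214 bleeds in 107 patient-years (rate 2) and a = 1.
- Exact Poisson: 1.74 to 2.29.
- Patient-level, log scale: SE = √(3/214) = 0.118; t quantile on 106 df = 1.983; factor exp(1.983 × 0.1184) = 1.265; limits 2/1.265 = 1.58 and 2 × 1.265 = 2.53.
- Planned interval for mean bleeds per patient: SD = √(2 + 1 × 4) = 2.45; SE = 2.45/√107 = 0.237; limits 2 ± 1.983 × 0.237 = 1.53 to 2.47.

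The second and third have almost the same width (0.95 and 0.94). The first has 0.55.

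**Step 3: does the mean-bleeds interval serve as an annual one?** Two follow-up patterns were tried. Short follow-up is uniform on 0.1-1 year (mean 0.55) and extended follow-up is uniform on 1-1.5 years (mean 1.25).
- 10% short, 15% extended: mean follow-up 1 − 0.10 × 0.45 + 0.15 × 0.25 = 0.99 years. Coverage of the annual rate at r/a of 1/0.5, 2/1 and 5/2 is 94%, 94% and 93%.
- 25% short, 25% extended: mean 1 − 0.25 × 0.45 + 0.25 × 0.25 = 0.95 years. Coverage is 90%, 89% and 89%.
- The second pattern rescaled to a mean of 1 year, equally uneven: 93-95%.

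The shortfall therefore comes from mean follow-up differing from one year, not from unevenness. Dividing the interval by mean follow-up gives an annual interval around exactly total bleeds over total follow-up, and in simulation it covers 92-97%.

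**Step 4: group contrasts.** With two groups of 53 and 54 and equal true rates, the exact Poisson intervals fail to overlap in 2.1%, 10.7% and 40.5% of datasets at 1/0.5, 2/1 and 5/2. Patient-level intervals fail to overlap in under 1%. With no between-patient variation (rate 2) the Poisson figure is 0.5%. Non-overlap is not a SAP criterion; it stands here for what a reader may do by eye.

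**The case against.** The strongest reply is that the study is descriptive, and that for the average rate of the enrolled patients a Poisson interval is legitimate if bleeds are independent. That stands. A reader might infer that the planned interval is simply wrong; the documents do not support this. Protocol 6.9 itself urges caution in generalising.

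The second reply is that the plan already shows the between-patient spread, through the mean-bleeds interval with its SD, quartiles and range, in the same subgroups. This also stands. With total person-years displayed beside the ABR, a reader could annualise that interval by one division. It would be wrong to say that the plan hides the variation, or that the mean-bleeds interval fails because follow-up is uneven (step 3). What remains is that the narrower of two intervals for nearly the same quantity is the one attached to the ABR.

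Third, a reader might infer that the plan will declare false group differences. No ABR test is named. The Poisson interval is specified overall, by site and by type; Poisson intervals within activity and severity groups are a plausible reading of the subgroup line, not an explicit statement.

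Fourth, the low coverage figures depend on assumed rates and dispersions. At dispersion 0.1 the loss is slight at rate 1 and modest at rate 5. The 44% cell is the bad end of a range, not an expectation.

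**Conclusion.** The point holds, at minor severity. The direction is certain: for any reading beyond these patients, or any contrast between groups of patients, the exact Poisson interval is too narrow whenever patients differ in their underlying rates. The size is not known from the documents. Over the assumed rates (1 to 5 per year) and dispersions (0.1 to 2) tabulated, coverage of the nominal 95% interval is about 94% down to 44%, and for rare site or type rates the effect is small. These figures rest on the gamma-Poisson model and the follow-up patterns above. The point estimate, the primary objective and every planned test are unaffected.

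A separate clarification lends no weight to this conclusion. In its definitions of bleed types, Protocol 6.4.1 lists procedure- or surgery-related bleeds as an assessed category but then says that they do not count as bleeds, while SAP 4.4.2 analyses them as a type. Neither document says whether the overall count and the ABR include them.

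**What to change.** Keep total bleeds over total follow-up as the estimate. Replace its interval, overall and in any activity or severity subgroup where one is shown, with a pre-specified patient-level interval on the annual rate. One suitable form is an intercept-only Poisson model with one record per patient, a log follow-up offset and patient-clustered robust variance, with limits on the log scale and a t quantile on patients minus one df. At minimum, divide the planned mean-bleeds interval by mean follow-up.

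Where bleeds are too few for a robust variance, keep the exact Poisson interval and label it as assuming independent bleeds. Fix the threshold in advance. Fewer than 10 bleeds is one workable choice: with 3 to 30 expected bleeds the combined rule covered 94-99% at n = 107 and 90-98% at n = 25. The cost of such a rule is that interval types can differ between rows of one table.

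The overall cost is two or three SAP sentences and a standard SAS procedure. Intervals become wider, and coverage is slightly short in small subgroups: 92.5-95% for the clustered interval in groups of about 25, and 88-92% for the divided mean-bleeds interval in groups of about 18.

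Separately, reconcile Protocol 6.4.1 with SAP 4.4.2 by stating whether procedure- or surgery-related bleeds enter the overall count and the ABR.
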